Baylor Institute for Rehabilitation Institutional Review Board

Protocol Template (for Investigator Initiated Studies)

Title: Group Lifestyle Balance Adapted for Impaired Mobility (GLB-AIM): Translating the GLB to Promote Healthy Weight in People with Mobility Disability (Impairment)

1. Introduction and Purpose:

This study will test **the effectiveness of the Group Lifestyle Balance**™ (GLB) program **adapted specifically for people with impaired mobility** using standard behavioral approaches for weight loss. The overarching aim of this study is to promote health and reduce chronic disease risk among people with mobility impairment by building an evidence base for weight loss. Our central hypothesis is that participants randomized to the intervention arm of the adapted GLB will show significant improvements on primary outcomes of weight and PA compared to a 6-month wait-list control group at 3 and 6 months, and will show improvements on several secondary health outcomes.

We propose the following specific aims and hypotheses:

Aim 1: To create an appropriate and usable adaptation of the GLB program for people with mobility impairment.

Hypothesis 1.1: Advisory board participants will identify key adaptations to make the GLB materials appropriate and usable for individuals with impaired mobility.

Aim 2: To establish whether the adapted GLB program for people with mobility impairment is a feasible intervention.

Hypothesis 2.1: Intervention participants will rate the program satisfactorily and attend at least 2/3rd of the weekly group-based meetings and monthly individualized phone calls. Lifestyle coaches will also rate the adapted program satisfactorily.

Aim 3: To determine if the GLB intervention adapted for those with mobility impairment is effective as determined by significant improvement in the primary and secondary outcomes in the intervention group compared to the wait-list control group at 3 and 6 months from baseline.

Hypothesis 3.1: The intervention group will demonstrate significantly greater improvements in our primary outcomes (weight and PA) than the wait list control group at 3 and at 6 months and will show significant improvements in secondary outcomes at 6 months.

Hypothesis 3.2: Both groups combined will demonstrate significantly greater improvements in the primary outcomes (weight and PA) after 3, 6 and 12 months of intervention and secondary outcomes after 6 and 12 months of intervention.

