The study will take place over 3 years and consists of two phases. Phase 1 will involve using community-based participatory research (CBPR) to adapt the evidence-based GLB program to assure the needs of people with mobility impairment are appropriately addressed. Phase 2 will consist of a RCT to assess feasibility and effectiveness of the adapted GLB program on primary (i.e., weight and PA) and secondary health outcomes (i.e., waist circumference, upper arm circumference, BP, A1c, serum lipids, self-efficacy, function, and QOL). In Phase 2, 64 individuals (32 per group) with physical disabilities will be recruited via organizations that provide services to those with disabilities and randomized to an intervention group or a 6-month wait-list control group. To ensure the participation of 64 individuals, up to 75 eligible individuals will be consented. We expect to obtain sufficient participants to enroll everyone with the same start date, but if necessary, the study may be conducted among 3 cohorts with staggered start dates.

Phase 1. Adapting the GLB and assessing usability. We will use CBPR to adapt the GLB in iterative fashion guided by input from a 12-member **Advisory Board** comprised of community stakeholders. Members represent people with mobility impairment from the independent living community and scientists, plus health professionals. Board members will receive a small honorarium for their time.

The board will guide the team's efforts in adapting the GLB materials and content in year 1 and provide ongoing input and direction over years 2 and 3 as the team delivers the intervention and assesses its effects.

Phase 2. Assess feasibility and effectiveness of the adapted GLB for people with mobility impairment. A two-group (experimental and wait-list control), RCT will assess feasibility of delivering the intervention and its effectiveness on primary and secondary outcomes. Those assigned to the **control group** will wait 6 months before receiving the intervention. During the 6 month waiting period, the control group will be mailed monthly newsletters that address topics of making healthy lifestyle choices (achieve good sleep; reduce stress; spend time with friends; follow recommended schedule of vaccines & cancer screening; reduce risk of common conditions such as pain, depression; know your rights).

GLB intervention.

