 - 2) Invited to participate in teleconference-based group meetings, delivered in accordance with the GLB schedule and led by a trained lifestyle coach; meetings will be offered via a videoconferencing technology, such as Adobe Connect, which allows people to connect by landline, cell phone, tablet, or computer and connect either via audio alone or audio and video.
 - **3)** Invited to an optional in person meeting each month, during which participants can be weighed;
 - 4) Offered monthly individualized phone support from a lifestyle coach;
 - 5) Invited to include caretakers or key family support in meetings, if desired
 - **6)** Offered exercise aids that are appropriate for individuals with impaired mobility, including disability appropriate exercise DVDs, Garmin vivofit arm-based exercise trackers with heart rate monitors, pedal exercisers, and therabands (versus the GLB's offering of nonmodified exercise DVDs, pedometers, and other incentives). Participants will also be given Calorie

King™ calorie counting books, measuring cups, and a scale, in accordance with the mainstream GLB.

Conditions that may result in the subject exiting the study before the expected completion date include subject withdrawal of consent or decision not to continue their participation. Because of the remote nature of the intervention, participants may choose to continue the study despite adverse health events including hospitalization. However, participants will be explicitly advised to follow their doctors orders in all matters, including those most relevant to the study—physical activity and diet.

Outcome measures.

Feasibility measures will assess participants' adherence with key intervention components: **1)** group meeting attendance, **2)** individualized phone call attendance, and **3)** for the first 12 weeks only, self-monitoring of food intake and PA.

Effectiveness measures. **Primary outcomes** to assess the GLB effects will be collected at baseline and again at 3, 6, and 12 months. These will include participant's weight, PA, self-efficacy, function, and QOL. **Secondary outcomes** will be measured at baseline, 6, and 12 months and will include waist circumference, BP, A1c, serum lipids.

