Baseline, 6 months, and 12 months:

- 1) Study staff will measure participants' blood pressure using an automatic cuff (Omron 7 Series wrist blood pressure monitor); upper arm circumference, and waist circumference measured at the umbilicus, with participants in a supine position when possible. Participants who have higher level injuries and/or difficulties in lying down will be measured in a seated position, or if they choose, transferred to the mat using a Hoyer lift.(34) Patients who do not require a Hoyer lift but who do require assistance in transferring from their chair will to a mat table can choose to be assisted by study staff, who have been trained by physical therapists in performing transfer assists.
- 2) A phlebotomist will draw participants' blood via venipuncture, and a UTSW lab will measure serum lipids to assess cardiovascular disease risk, A1c to assess participants' average blood sugar level over the past 2-3 months, and albumin to assess blood protein levels and nutritional status. The total volume of blood drawn will be 10mL, collected in 2 vials of 4-5 mL each.

Baseline and final visit (12 months for experimental group, 18 months for control):

 In addition to the above, participants will be asked to answer paper/pencil survey questions to assess the following: functional abilities in activities of daily living and instrumental activities of daily living (using the LIFE-H short form questionnaire);

- functional abilities around diet, eating, and fitness (using portions of the LIFE-H long form); and types of physical activities (using the 1-year MAQ).
- 2) Structured interviews with participants, conducted either in person or by phone, will gather qualitative information on topics such as motivation for joining the program; past weight loss experiences; who selects, purchases, and prepares food in the home; changes in these roles over time; the process of lifestyle change and its effects on sense of self and relationships; and barriers and facilitators to change. Similar questions may be asked and responses gathered during one or more of the monthly individualized phone support calls throughout the course of the program. Interviews may be recorded to ensure participant responses are accurately captured.

Final visit only:

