14. Biostatistics: We will use univariate analysis to summarize the measures of program usability and feasibility and examine their distributional properties (Aims 1 & 2). General/generalized mixed modeling analysis(41, 42) will be conducted for the primary and secondary effectiveness outcomes, to assess initial and sustained impacts of the adapted GLB intervention (Aim 3). More specifically, we will evaluate individual growth models for linear/nonlinear change from baseline to 6 months (level-1, time effects), overall group difference (level-2, group effect), and group difference in change (crosslevel, time-by-group interaction effect) (Hypothesis 3.1). Models will be adjusted for demographic variables (e.g. age, gender, ethnicity, disability severity, etc.), particularly if they are imbalanced after randomization, thereby providing more accurate estimates of the intervention impacts. We will also fit separate individual growth models for change from baseline to 12 months within both groups combined (time effects only) (Hypothesis 3.2). Our data will include missing observations due to either attrition or nonresponse. Intent-to-treat analysis will use restricted maximum likelihood estimation, which can produce unbiased estimates under the conditions of incomplete data. Subsequent intent-totreat analysis will utilize iterative Monte Carlo Markov Chain multiple imputation. (43) This approach includes all selected variables into the imputation process, which allows for greater recovery of the missing data.(44) All analyses will be performed using R(45) and SAS 9.3.(46) Secondary analyses will examine intervention effects for study completers who meet defined program adherence criteria.

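### Function is scheduled at 3, 6 and 12 months in section 3, but the visit list gives LIFE-H only at baseline and the final visit, which would remove the 6-month comparison with wait-list for function.

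*Combined protocol and SAP*

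**What the plan says.** Section 3 (Outcome measures) lists the primary outcomes as "weight, PA, self-efficacy, function, and QOL" and says that they "will be collected at baseline and again at 3, 6, and 12 months". Earlier in section 3, the project summary instead places function among the "secondary health outcomes (i.e., waist circumference, upper arm circumference, BP, A1c, serum lipids, self-efficacy, function, and QOL").

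Under either label, a comparison with wait-list within the first 6 months is planned. Aim 3 in section 1 is to be judged on "primary and secondary outcomes in the intervention group compared to the wait-list control group at 3 and 6 months from baseline". For the secondary outcomes, Hypothesis 3.1 names 6 months. Section 14 models change from baseline to 6 months and tests the "group difference in change (crosslevel, time-by-group interaction effect) (Hypothesis 3.1"). Hypothesis 3.2 adds a combined-group analysis of "secondary outcomes after 6 and 12 months of intervention".

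The visit list in section 4 differs. Under "Baseline and final visit (12 months for experimental group, 18 months for control") it places the survey of "functional abilities in activities of daily living and instrumental activities of daily living (using the LIFE-H short form questionnaire"), together with portions of the LIFE-H long form and the 1-year MAQ. The questionnaire for all visits contains the IPAQ short form, SRAHP and SF36E. The block for baseline, 6 and 12 months contains only physical and blood measures.

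**The concern.** The two schedules cannot both be followed, and the protocol does not say which takes precedence. Staff who run visits would naturally work from the visit list. If they do, function has only a baseline value during the period when the randomised arms differ in treatment. The planned group comparison for this outcome would be lost, and the gap could not be filled later, because the wait-list arm starts the intervention after month 6. The combined-group analysis is also weakened: the wait-list arm would have no function value at the start of its own intervention, so its change would mix untreated and treated time.

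**Working it through.** The plan gives no figure to reproduce on this point. The check sets the schedules side by side.

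**Inputs.** LIFE-H months from baseline come from the section 4 visit list. The control arm waits 6 months before the intervention (section 3). Control visits fall at months 0, 3, 6, 9, 12 and 18 (section 4). Each arm has 32 participants, and the highest attrition seen in earlier studies was 23% at 6 months and 33% at 12 months (section 14).

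**Schedule by arm if the visit list is followed.**

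| | Experimental | Wait-list |
|---|---|---|
| LIFE-H, months from baseline | 0, 12 | 0, 18 |
| LIFE-H, months from start of intervention | 0, 12 | -6, 12 |
| LIFE-H at month 3 or 6 from baseline | none | none |
| LIFE-H after 6 months of intervention | none | none |

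**Hypothesis 3.1.** The section 3 schedule gives two follow-ups in the window (months 3 and 6). The visit list gives none in either arm. A model of change from baseline to 6 months needs at least one value after baseline, so neither the time effect nor the time-by-group effect can be estimated. The restricted maximum likelihood and multiple imputation planned in section 14 do not help: the 6-month value is missing by design for every participant, so any imputed value would rest wholly on assumption.

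**Any other randomised comparison.** The arms share no time point after baseline (12 against 18 months). The only wait-list follow-up comes after 18 - 6 = 12 months of intervention. No comparison with an untreated control is therefore available at any time.

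**Hypothesis 3.2.** No value exists after 6 months of intervention in either arm. The wait-list interval is 18 months, of which 6/18 = 33% is untreated; the experimental interval is 12 months, all treated.

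**What a month-6 LIFE-H would give.** Between 32 × (1 - 0.23) = 24.6, about 25, and 32 participants per arm, instead of 0.

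**The case against.** The strongest objection is that no sentence equates the outcome function with LIFE-H. Section 3 names constructs and section 4 names instruments. SRAHP and SF36E are given at every visit, and if one of them were meant to measure function, the 6-month data would exist. This is a fair caution, and the stated loss depends on it. But section 4 labels SRAHP as self-rated health abilities and SF36E as quality of life, section 3 lists function separately from self-efficacy and quality of life, and only LIFE-H is described as measuring functional abilities. If another instrument is intended, the protocol has to name it, so a correction is needed in either case.

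A second objection is that the stakes are limited. Function lies outside the power calculation, the hypotheses in section 1 name only weight and physical activity as primary, and section 7 calls the study a pilot. This stands, and it keeps the point below the level of a threat to the main result.

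Third, the primary/secondary conflict is wider than function: self-efficacy and quality of life are also primary in one part of section 3 and secondary in another. That is correct, and all three should be settled together.

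None of these objections removes the conflict between the two schedules.

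**Conclusion.** The concern holds. Sections 3 and 4 contradict each other on when function is measured. If the visit list is followed and LIFE-H is the function measure, 0 of 2 arms have a value after baseline by month 6 and 0 of 2 have a value after 6 months of intervention. The randomised comparison for function is then lost entirely, and the wait-list pre-post change is one-third untreated time. The analyses of weight and physical activity are unaffected. This should be fixed before month-6 visits begin, since a missed month-6 value cannot be collected afterwards. Confidence in the contradiction is high. The one inference is that LIFE-H is the function instrument, which is the natural reading but is not stated.

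**What to change.** Reconcile the two schedules and name the instrument, including which LIFE-H form, that defines function.

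**Preferred.** Give at least the LIFE-H short form at the month-6 visit in both arms and at the month-12 visit in the wait-list arm. Month 6 supplies the randomised contrast and the wait-list value before intervention; wait-list month 12 supplies its value after 6 months of intervention. The 1-year MAQ and the interviews can stay at baseline and final visit. Remove the 3-month function entry from section 3 unless LIFE-H is also given then, and align Aim 3 with Hypothesis 3.1 on the timing of secondary outcomes. State whether function, self-efficacy and quality of life are primary or secondary.

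**Cost.** All these visits already exist. Extra questionnaires: 32 × 1 + 32 × 2 = 96 at full retention. With the section 14 attrition maxima, 24.6 + 24.6 + 32 × 0.67 = 24.6 + 24.6 + 21.4, about 71. This is indicative only: the rates come from earlier studies, and the 12-month rate is applied to a wait-list visit that follows 6 untreated months. The protocol gives no LIFE-H completion time. Assuming 15 to 30 minutes, the form takes 25% to 50% of a visit planned at about 1 hour, or 96 × 0.25 = 24 to 96 × 0.5 = 48 participant-hours in total. Mailing the form ahead, as is planned for the exit survey, would shorten the visit but not the participant's time.

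**If that burden is not acceptable.** Delete both the 3- and 6-month function entries from section 3. State that function is excluded from the between-group comparison in Aim 3 and Hypothesis 3.1 and from the 6-month part of Hypothesis 3.2. Report it only as within-group change, noting that the wait-list interval includes 6 untreated months. This costs no visit time but gives up the randomised comparison for function.

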1) Participants will be asked to complete a paper/pencil exit survey(36) to obtain participants' satisfaction, perceived benefits and barriers of the intervention, and recommendations to improve it. The survey will be mailed in advance and returned at this visit or by mail, if participants for some reason are unable to return.

Travel monies for transportation costs for assessments will be made available for participants without access to transportation.

Intervention delivery

Staff training. Lifestyle coaches will complete training at the 2-day GLB workshop conducted by [name] and the faculty of the DPSC at the University of Pittsburgh. The DPSC will listen in on the first 3 group-based teleconference calls to monitor fidelity and also offer ongoing support and guidance to lifestyle coaches through regularly scheduled calls for problem solving and e-mail communication as needed.

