Sample size and power. Sample size was determined to provide sufficient power for our analyses on the primary outcomes. Previous studies showed that in general DPP translation efforts including the GLB yield large impacts on weight (median d = 0.99 at 3 months, 0.91 at 6 months, 0.74 at 12 months(16, 17, 19-21, 27, 47-49)) and relatively large impacts on PA (d = 0.69 at 3 months(20)). Results also indicated, at most, 16%, 23%, and 33% attrition at 3, 6, and 12 months, respectively. A sample size of 64 will allow greater than 90% power to detect a conservatively assumed group difference of 4% in weight change (95% power) and 80 min./week in PA (92% power). In the event of 33% attrition (the maximum observed in previous GLB studies), we will achieve 83-87% power to detect these differences. Thus, 64 participants (32 per group) will be enrolled.

References

- 8. Centers for Disease Control and Prevention. Physical activity among adults with a disability-United States, 2005. Morbidity and Mortality Weekly Report 2007;56(39):1021-1024.

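### Satisfaction is surveyed only at the final visit, with no provision for participants who stop the programme earlier, so the satisfaction part of Hypothesis 2.1 is likely to over-represent stayers

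*Combined protocol and SAP*

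**What the plan says.** Section 1 makes feasibility a primary study endpoint alongside effectiveness. Hypothesis 2.1 states the feasibility criterion: "Intervention participants will rate the program satisfactorily and attend at least 2/3rd of the weekly group-based meetings and monthly individualized phone calls". It adds: "Lifestyle coaches will also rate the adapted program satisfactorily".

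Section 4 describes one instrument for participant satisfaction, a paper exit survey that also collects "perceived benefits and barriers of the intervention, and recommendations to improve it". It stands under the heading "Final visit only". The heading before it shows when that visit falls: "Baseline and final visit (12 months for experimental group, 18 months for control". The form is posted beforehand and may be handed in at the visit, or sent back by post if the participant cannot come.

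Section 3 gives the reasons for leaving the study early, including "subject withdrawal of consent or decision not to continue their participation". No survey or interview is linked to that event. Section 4 schedules structured interviews, which include barriers and facilitators, at baseline and the final visit. It permits, but does not require, similar questions on the monthly coach calls.

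Section 14 plans univariate summaries of usability and feasibility. Restricted maximum likelihood and multiple imputation are described for the effectiveness analyses. No rule is given for exit surveys that are not returned.

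**The concern.** Dissatisfaction, or a barrier that could not be overcome, is a plausible reason to stop a year-long lifestyle programme. If the rating is requested only at the end, whether it is missing may depend on what the rating would have been. A summary of the returned forms would then tend to be too favourable.

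This matters because section 1 presents the study as groundwork for a large randomised trial. An inflated satisfaction score would make the programme look more acceptable than it was to the people who began it. The views of those who left, which are among the most useful findings for planning the next trial, would be collected least systematically.

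**Working it through.** The plan states no sample size, threshold or power for the satisfaction rating, so there is no figure of its own to reproduce. The check has two parts.

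**1. Who is asked.** Three provisions could reach a participant who stops at, say, month 4.
- *Exit survey:* tied to month 12 or 18, with no trigger at discontinuation.
- *Mail return:* a way of sending back the final-visit form. The text does not say that people who have already exited are sent one, and does not rule it out.
- *Coach calls:* optional questions, asked only while the person still takes calls. The listed interview topics include barriers but not satisfaction.

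None of the three commits the study to obtaining a rating from someone who stopped.

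**2. How much it could matter.**

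Inputs from the documents:
- 32 participants per arm (section 14).
- Earlier-study attrition of "at most, 16%, 23%, and 33% attrition at 3, 6, and 12 months" (section 14).
- Pilot satisfaction mean of 6.2 out of 7 (section 2).

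Assumptions, not in the documents:
- Stayers average the pilot value, on the pilot's 7-point scale.
- Leavers would average between 3 and 5.
- No leaver returns a form by mail.

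Formulas, with *d* the unrated share and *m* the leavers' mean:
- unrated per arm = 32 × *d*
- mean over all starters = (1 − *d*) × 6.2 + *d* × *m*
- overstatement if only stayers are summarised = *d* × (6.2 − *m*)

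| *d* | Unrated of 32 | All-starter mean, *m* = 3 | All-starter mean, *m* = 5 |
|---|---|---|---|
| 0.16 | 5.12 | 5.69 | 6.01 |
| 0.23 | 7.36 | 5.46 | 5.92 |
| 0.33 | 10.56 | 5.14 | 5.80 |

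At *d* = 0.33:
- *m* = 3: 0.67 × 6.2 + 0.33 × 3 = 4.154 + 0.99 = 5.14
- *m* = 5: 4.154 + 1.65 = 5.80
- Overstatement: 0.33 × 3.2 = 1.06 down to 0.33 × 1.2 = 0.40 scale points

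The outer limits at 33% are 0.67 × 6.2 + 0.33 × 1 = 4.48 if every leaver would have given 1, and 6.2, with no bias, if leavers would have rated like stayers.

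The 33% fits the experimental arm best. Wait-list members have had only six months of programme by month 12, and the plan gives no 18-month attrition figure. Those lost before month 6 never started the programme and have nothing to rate.

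**The case against.** The strongest reply is that the gap is narrow. Most of this stands.

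- **Mail return.** The wording is open-ended, and attending is not a condition for being rated. A reader might infer that everyone who stops early goes unrated. The documents do not support that; some leavers could be reached. But the route belongs to the final visit, and nothing says that a person who exited months earlier is sent the form.
- **Other feasibility evidence.** A reader might infer that the whole feasibility verdict rests on people who stayed 12 months. It does not. Section 3 defines the feasibility measures as group attendance, phone-call attendance and self-monitoring over the first 12 weeks, all recorded as the programme runs. Hypothesis 2.1 also requires two-thirds attendance and includes coach ratings. Favourable satisfaction alone cannot satisfy it.
- **Barriers.** It would be too strong to say that reasons for leaving never reach the team. Coach calls may cover barriers, study staff deliver the programme themselves, and the advisory board gives continuing input. These channels are informal or optional and do not replace a rating.
- **Stopping sessions is not leaving the study.** The planned intent-to-treat analysis implies that non-adherent participants can still be assessed, and some may complete the survey. Some who withdraw consent may be out of reach under any plan.
- **Size.** Applying 33% to all 64 gives about 21 unrated, but that counts wait-list members who may have left before starting. The 33% is a maximum from earlier studies, and the leavers' ratings are assumed.

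An end-of-programme survey is a sensible way to rate a complete curriculum. The point concerns only those who do not reach the end.

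**Conclusion.** The concern holds for the satisfaction part of Hypothesis 2.1 only. As written, the plan makes no provision for rating participants who stop the programme early, so the summary is likely to lean towards those who stayed.

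In the worst case, up to about 11 of 32 per arm are unrated, given 33% attrition and no mail returns; for the wait-list arm this must exclude people lost before month 6. The size of the bias cannot be fixed from the documents, because they give neither leavers' ratings nor mail-return rates. Under the stated assumptions, the mean over all starters would be about 5.1 to 5.8 where stayers alone give 6.2. These figures illustrate a possible bias and do not predict what the trial will report.

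**What to change.** In section 4, offer the same exit survey, on a voluntary basis and by the existing mail route or by phone, to each participant when they stop the programme, and to everyone else at the final visit.

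In section 14:
- summarise satisfaction over all who started the programme, leaving out wait-list members lost before month 6;
- report return rates and ratings separately for stayers and leavers;
- state that the satisfaction part of Hypothesis 2.1 will not be concluded from final-visit respondents alone.

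Counting non-responders as not satisfied may be shown only as a worst-case bound, since people also leave for unrelated reasons. It would need a cut-off for a satisfactory rating, which the plan does not give.

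The cost is a short amendment and a few extra mailings or calls. Response from leavers will be incomplete, and the reported satisfaction may be lower. Sample size, visit schedule and effectiveness analyses do not change.
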